## **14.2 Sample Size Justification and Analysis Plan**

Previous studies of the skin transcriptomes have estimated approximately 13,000 genes per biopsy of healthy individuals [18]. This large number of genes will be examined to find a smaller list of differentially expressed genes within cohorts. To analyze the data, non-normalized raw counts will be used with an analysis program (e.g., the EdgeR package) to perform differential gene expression analysis after quality control of samples. Our anticipated analysis program will utilize model-based scale normalization, estimate dispersions, and apply a negative binomial model for RNA transcriptomic data analysis to find differentially expressed genes.

Single comparisons will be made within cohorts of bitten skin at a particular timepoint to the unbitten skin biopsy. Because our study will analyze paired samples (bitten skin and unbitten skin biopsies from the same individual), we can employ two different approaches. First, we can apply general linear modelling (GLM) using a GLM likelihood ratio test for comparing bitten versus unbitten skin. Also, we can employ group-wise comparisons where negative binomial fitting is followed by exact test. FDR adjustment will be used for multiple testing correction. An FDR threshold of 0.1 for statistical significance is typically applied. Genes with larger differential expression will be defined with a log-fold-change threshold of 0.5 (i.e., 50% change between experimental conditions).

Currently it is unknown how uniform skin immune responses to bites of these vector are and how much variability will be observed. Therefore it is very difficult estimate an exact samples size. As this study is very exploratory in nature it is likely with the relative small number of individuals in each cohort the results will be very informative of future studies as it will offer more insight into the diversity or lack thereof in the skin responses. The cohort sizes of 15 will allow of us to have adequate numbers to perform these detailed and expensive immunohistochemical and transcriptomic techniques that could lead to future larger studies with more focused testing once the differential genes and important areas of immune response are identified.

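### Section 14.2 equates a log-fold-change of 0.5 with a 50% change, gives no log base, and the two agree on no standard base (1.41-fold on log2, 1.65-fold on natural log)

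*Combined protocol and SAP*

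**What the plan says.** The cut-off appears once, in section 14.2 of the combined protocol and SAP: "Genes with larger differential expression will be defined with a log-fold-change threshold of 0.5 (i.e., 50% change between experimental conditions". The sentence defines a class of genes, and it presents the percentage as the meaning of the number rather than as a rough guide.

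The surrounding text does not settle the scale. The software is named only as an example: "non-normalized raw counts will be used with an analysis program (e.g., the EdgeR package) to perform differential gene expression analysis". The fold change applies to bitten against unbitten skin: "Single comparisons will be made within cohorts of bitten skin at a particular timepoint to the unbitten skin biopsy". Significance is a separate criterion: "An FDR threshold of 0.1 for statistical significance is typically applied". No other section gives a log base or repeats the threshold.

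**The concern.** A threshold on a log scale has no meaning until the base is known, and here the percentage beside it does not supply the base, because no base in ordinary use reconciles the two. A reader who follows the number and a reader who follows the percentage will apply different cut-offs, and both can claim to follow the plan.

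Skin transcriptomics is part of the primary endpoint in both cohorts (section 3.2.1, items 1b and 2b). Section 14.2 aims to reduce about 13,000 genes per biopsy to a shorter list of differentially expressed genes, and expects later, more focused studies to build on what is found. This threshold is the section's only effect-size criterion. At stake are which genes carry the label of larger differential expression, and whether the label is true when reported.

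**Working it through.** **Inputs, all from section 14.2.** Threshold 0.5; stated meaning, a 50% change; log base, not stated. Bases 2, e and 10 are tried in turn as assumptions.

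**Formulas.** Fold change up = base^0.5. Fold change down = base^(−0.5). Threshold needed for a 50% increase = log_base(1.5). Threshold needed for a 50% decrease = log_base(0.5).

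**Can the plan's 50% be reproduced?**

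| Base | 0.5 up | 0.5 down | Log value of 1.5-fold | Log value of a halving |
|---|---|---|---|---|
| 2 | 2^0.5 = 1.414 (+41.4%) | 2^(−0.5) = 0.707 (−29.3%) | 0.585 | −1.000 |
| e | e^0.5 = 1.649 (+64.9%) | e^(−0.5) = 0.607 (−39.3%) | 0.405 | −0.693 |
| 10 | 10^0.5 = 3.162 (+216.2%) | 10^(−0.5) = 0.316 (−68.4%) | 0.176 | −0.301 |

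No row gives 50% in either direction. Solving backwards, base^0.5 = 1.5 requires a base of 1.5² = 2.25, and base^(−0.5) = 0.5 requires a base of 0.5^(−2) = 4.

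**Where 50% might come from.** The figure follows from 0.5 only if 0.5 is read as an unlogged proportion, which contradicts calling it a log-fold-change, or through the small-change approximation ln(1 + x) ≈ x. At x = 0.5 that approximation is poor: a natural-log value of 0.5 is +64.9%.

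**Size of the gap, taking the intended meaning as 1.5-fold up or down (1/1.5 = 0.667, so +50%/−33%).**

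- log2: 1.4142/1.5 = 0.943, so the cut-off is 5.7% below 1.5-fold. Genes with an absolute log2 fold change between 0.500 and 0.585 (up 41% to 50%, or down 29% to 33%) pass the number but not the stated percentage.
- Natural log: 1.6487/1.5 = 1.099, so the cut-off is 9.9% above 1.5-fold. Genes with an absolute natural-log fold change between 0.405 and 0.500 (1.5- to 1.65-fold) meet the percentage but fail the number.

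**If a decrease is instead read literally as a 50% fall.** The threshold for decreases would be an absolute value of 1.0 on log2 or 0.693 on natural log. A cut-off of 0.5 would then admit genes down 29% to 50% on log2, or down 39% to 50% on natural log, that do not meet the stated percentage.

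**The case against.** The strongest defence is that little depends on the sentence. The threshold marks a descriptive tier; significance rests on the FDR. The hypothesis in section 14.1 and the sample-size discussion do not use it, section 14.2 contains no power calculation, and section 14 describes the study as highly exploratory. Mislabelling on log2 also requires someone to carry the percentage into the report, and the documents do not say that results will be expressed that way. All of this stands. It limits the severity but does not make the sentence correct.

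A second objection is that the base is obvious from the example program. The documents do not fix the program, and granting log2 would not help, since 0.5 would then be +41%.

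A third is that the size of the discrepancy depends on how a 50% change is read for decreases. That is fair: the plan gives no direction, and the downward bands differ between the 1.5-fold reading and the literal halving. Neither reading rescues the sentence, but it is a reason to state both directions in the correction.

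A fourth is that a correction written only on log2 presumes a base the plan does not give. This also stands, so the fix must leave room for natural log. Finally, the documents do not show whether analysis has begun, so correction beforehand may no longer be possible.

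**Conclusion.** The concern holds as a minor error. The number and its stated meaning in section 14.2 disagree on log2, natural log and log10, and naming the base would not by itself cure this. If log2 was meant, the cut-off is 1.41-fold, and genes between 1.41- and 1.5-fold would be listed under a percentage they do not reach. If natural log was meant, the cut-off is 1.65-fold, and genes between 1.5- and 1.65-fold would be left off a list said to start at 50%.

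These bands assume that a 50% change means 1.5-fold in either direction. The documents give no distribution of fold changes, so the number of genes in either band cannot be stated, and nothing shows that a conclusion would change. The effect is confined to the effect-size label in the skin transcriptomic analyses. The FDR criterion, the hypothesis, the sample size and the immunohistochemistry are unaffected.

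**What to change.** Replace the sentence with one that states the base, the threshold on that scale, and the matching change in each direction. If the base is log2, either of these is coherent:

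- absolute log2 fold change of at least 0.585, meaning at least 1.5-fold up or down (+50%/−33%);
- absolute log2 fold change of at least 0.5, meaning at least 1.41-fold up or down (+41%/−29%).

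If natural log was intended, the equivalents are 0.405 for 1.5-fold, or 0.5 described as 1.65-fold (+65%/−39%). The sponsor should say which figure, the number or the percentage, was intended. If a 50% fall is meant literally for decreases, a separate threshold for decreases is needed.

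The choice should be made before the data are analysed, so that it cannot be influenced by the gene list. If analysis has already been done, the report should give the base and cut-off actually used and drop the 50% description unless it is true of them.

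The cost is one sentence in section 14.2. On log2, moving to 1.5-fold gives a somewhat shorter labelled list, and keeping 0.5 means stating a less favourable percentage. On natural log, moving to 1.5-fold gives a somewhat longer list.

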## **15 Ethics/Protection of Human Participants**

### **15.1 Informed Consent Process**

Informed consent is a process where information is presented to enable persons to voluntarily decide whether or not to participate as a research participant. It is an ongoing conversation between the human research participant and the researchers, which begins before consent is given and continues until the end of the participant's involvement in the research. Discussions about the research will provide essential information about the study and include: purpose, duration, experimental procedures, alternatives, risks, and benefits. Participants will be given the opportunity to ask questions and have them answered.

The participants will sign the informed consent document prior to undergoing any research procedures. The participants may withdraw consent at any time throughout the course of the trial. A copy of the informed consent document will be given to the participants for their records. The researcher will document the signing of the consent form in the participant's medical record. The rights and welfare of the participant will be protected by emphasizing to them that the quality of their medical care will not be adversely affected if they decline to participate or withdraw from this study.

#### **15.1.1 Non-English-speaking participants**

If a non-English-speaking participant is unexpectedly eligible for enrollment, the participant will be provided with the CC Short Written Consent Form for Non-English-Speaking Research Participants in the participant's native language and a verbal explanation of the purpose, procedures, and risks of the study as described in NIH HRPP standard operating procedure 12, and 45 Code of Federal Regulations (CFR) 46.117(b)(2). The IRB-approved English consent form will serve as basis for the verbal explanation of the study. The investigator will obtain an interpreter unless the investigator is fluent in the prospective participant's language. Preferably, the interpreter will be someone who is independent of the participant (i.e., not a family member). Interpreters provided by the CC will be used whenever possible. The interpreters will interpret all oral communications (English to target language and conversely) between the investigator and a limited English-proficient participant, facilitate discussions, and clarify information as necessary.

The IRB-approved English consent form will be signed by the investigator obtaining consent and a witness to the oral presentation. The CC Short Written Consent Form will be signed by the participant and a witness who observed the presentation of information. The interpreter may sign the consent document as the witness and, in this case, will note "Interpreter" under the signature line. A copy of both signed forms will be provided to the participant to take home.

The investigator obtaining consent will document the consent process in the participant's medical record (CRIMSON), including the name of the interpreter. Further, all instances of use of the CC Short Written Consent Form will be reported to the IRB at the time of annual review. If the CC Short Written Consent Form is used three times or more for the same language, this will be reported to the IRB immediately.

#### **15.2 Participant Confidentiality**

All records will be kept confidential to the extent provided by federal, state, and local law. The study monitors and other authorized individuals may inspect all documents and records required to be maintained by the investigator, including but not limited to medical records. Records will be kept locked and all computer entry and networking programs will be done with coded numbers only. Clinical information will not be released without written permission of the participant, except as necessary for monitoring by the IRB, NIAID, and Office for Human Research Protections.

## **16 Data Handling and Record Keeping**

### **16.1 Data Capture and Management**

Study data will be collected and maintained in CRIMSON and the Clinical Research Information System (CRIS) and collected directly from participants during study visits and telephone calls, or will be abstracted from participants' medical records. Source documents include all recordings of observations or notations of clinical activities and all reports and records necessary to confirm the data abstracted for this study. Data entry into these systems will be performed by authorized individuals. The investigator is responsible for assuring that the data collected are complete, accurate, and recorded in a timely manner.

### **16.2 Record Retention**

The investigator is responsible for retaining all essential documents listed in the ICH GCP guidelines. Study records will be maintained by the PI according to the timelines specified in CFR 312.62 or a minimum of 5 to 7 years, and in compliance with institutional, IRB, state, and federal medical records retention requirements, whichever is longest. All stored records will be kept confidential to the extent required by federal, state, and local law.

**Appendix A: Schedule of Procedures/Evaluations**

Study Cohort	Cohort A			Cohort B					
Procedures/Evaluations	Study Days (window)								
	Day 0	Day 1 (+1 day)	Day 7 (±3 days)	Day 0	Day 14 (±7 days)	Day 28 (±7 days)	Day 42 (±7 days)	Day 44 (+3 days)	Day 51 (±3 days)
Informed Consent 	X			X					
Medical/Medication History	X			X	X	X	X	X	
Review of Eligibility Criteria	X			X	X	X	X	X	
Documentation of Usual Insect Bite Response	X			X					
Clinician Exam/Assessment	X	X		X	X	X	X	X	
Vital Signs 	X	X		X	X	X	X	X	
Urine Pregnancy Test 	X			X	X	X	X		
Blood Draw	X	X		X				X	
Vector Feeding	X			X	X	X	X		
Skin Punch Biopsy	X 						X 	X 	
Telephone Call to Assess Symptoms			X						X
Skin Biopsy Laboratory Evaluations									
Skin Immunohistochemistry	X						X	X	
Skin Transcriptomics	X						X	X	
Blood Laboratory Evaluations									
Post-feeding Labs (PBMC flow cytometry, plasma cytokine analysis, gene expression of circulating white blood cells)		X						X	

Abbreviations: RNA, Ribonucleic acid; PBMC, peripheral blood mononuclear cell

Informed consent will be obtained within 90 days of or at Day 0 prior to any study procedures. Screening is performed under protocol 11-I-0183.

Participants must be sitting for a minimum of 5 minutes prior to these procedures being performed; vital signs include blood pressure, mean arterial pressure, heart rate, respiratory rate, temperature, weight, and pulse oximetry; height will be taken at the Day 0 visit only. On days with feeding, vital signs will be performed pre-feeding.

Females of childbearing potential only. Insect feeding will not be initiated until results are available.

One biopsy from bitten skin will be collected no earlier than 30 minutes and no later than 90 minutes after the vector feeding is completed. One biopsy from bitten skin will be collected no earlier than 3.5 hours and no later than 4.5 hours after the vector feeding is completed. One biopsy will be collected from unbitten skin on the opposite arm no earlier than 30 minutes and no later than 6 hours after the vector feeding is completed.

 One biopsy from bitten skin will be collected no earlier than 3.5 hours and no later than 4.5 hours after the vector feeding is completed. One biopsy from unbitten skin on the opposite arm will be collected no earlier than 30 minutes and no later than 6 hours after the vector feeding is completed.

One biopsy will be collected from bitten skin at a minimum 40 hours after vector feeding is completed.

**Appendix B: Blood Volumes for Specimen Collection**

Study Cohort	Cohort A		Cohort B				
Evaluations	Study Days (window)						
	Day 0	Day 1 (+1 day)	Day 0	Day 14 (+7 days)	Day 28 (+7 days)	Day 42 (+7 days)	Day 44 (+3 days)
	Blood Volume in mL						
Post-Feeding Labs							
Whole blood	(10 mL X 5)	(10 mL x 5)	(10 mL X 5)	0	0	0	(10 mL x 5)
PAXGene tube	(2.5 mL X 1)	(2.5 mL x 1)	(2.5 mL X 1)	0	0	0	(2.5 mL x 1)
Daily Volume	52.5mL	52.5 mL	52.5mL	0	0	0	52.5 mL
Cumulative Volume	52.5 mL	105 mL	52.5 mL	0	0	0	105 mL
